3.3 Clinical and Non-clinical Information

3.3.1 Clinical Experience with Rifaximin Soluble Solid Dispersion Tablets

The pharmacokinetics of rifaximin were evaluated in four Phase 1 studies and one Phase 2 study after administration of the rifaximin soluble solid dispersion (SSD) formulation in either healthy volunteers or subjects with impaired liver function.

Study RFPK1042 was a 2-part study evaluating the pharmacokinetics of rifaximin SSD at different doses and the regional absorption and bioavailability of rifaximin following targeted release at prespecified locations in the GI tract. Study RNPK1002 evaluated the pharmacokinetics of the 80 mg rifaximin SSD tablet using 3 different release formulations. Study RNDI1005 is a drug-drug interaction study that evaluated whether esomeprazole, which raises GI pH, alters the PK of the IR and SER formulation of rifaximin when administered concomitantly. Study RNPK1003 evaluated the single-dose PK of rifaximin 80 mg IR and 80 mg SER dispersion tablets, as well as 80-mg and 80-mg SER administered together in subjects with mild, moderate, and severe hepatic impairment and in healthy subjects. Study RNLC2131 evaluated the population pharmacokinetics of rifaximin SSD tablets in subjects with liver cirrhosis who participated in the randomized, double-blind, placebo-controlled, dose-ranging, multicenter study to assess the efficacy and safety of rifaximin SSD tablets for the prevention of complications in subjects with early decompensated liver cirrhosis.

Overall, the results of the early Phase 1 studies demonstrated the safety and formulation performance of rifaximin SSD. Progressive decreases in systemic exposure as a function of increasing delays in intestinal release were observed for rifaximin SSD tablets.

Mean Cmax values ranged from 1.41 ng/mL to 5.20 ng/mL [for the sustained extended release (SER) and immediate release (IR) formulations, respectively]; corresponding mean AUC_{0-∞} values were 10.2 ng.h/mL and 24.9 ng.h/mL ([RNPK1002 CSR, Table 6](#)). Compared with the current 550 mg tablet formulation, rifaximin IR and SER tablet formulations provide similar or lower Cmax and AUC values systemically, accompanied by prolonged half-lives that may indicate increased GI residence times. The data demonstrate the feasibility of a single daily rifaximin IR or SER dose.

Phase 2 Program

Study RNLC2131 was a Phase 2, randomized, double-blind, placebo-controlled, multicenter study evaluating the efficacy (prevention of hospitalization for complications of liver cirrhosis or all-cause mortality in subjects with early decompensation) and safety of rifaximin SSD tablets in subjects with early decompensated liver cirrhosis. Subjects with documented medically non-refractory ascites who had not previously experienced spontaneous bacterial peritonitis (SBP), esophageal variceal bleeding (EVB), or hepatorenal syndrome (HRS) were enrolled in the study. Subjects completed a 1 to 21-day Screening Period, a 24-week Treatment Period, and a 2-week Follow-up Period. A total of 518 subjects who successfully completed the Screening Period entered the Treatment Period and were randomized in a 1:1:1:1:1:1 allocation to 1 of 6 treatment groups. All treatments were administered once daily at bedtime (QHS).

Subjects were treated QHS with rifaximin SSD, 40 mg or 80 mg tablets, in 1 of 2 formulations of IR and SER.

The active treatment groups were as follows:

- Treatment A: rifaximin SSD 40 mg QHS (IR tablet)
- Treatment B: rifaximin SSD 80 mg QHS (IR tablet)
- Treatment C: rifaximin SSD 40 mg QHS (SER tablet)
- Treatment D: rifaximin SSD 80 mg QHS (SER tablet)
- Treatment E: rifaximin SSD 80 mg (IR tablet) and SSD 80 mg (SER tablet) QHS

Overall, the mean MELD score was 11.5, with the majority of subjects (280 subjects; 54.3%) scoring between 11 and 18. The overall mean MELD score was 12.9, with the majority of subjects (327 subjects; 63.4%) again scoring between 11 and 18. Most subjects (416 subjects; 80.6%) had a class B Child-Pugh classification and a Conn score category of 0 (317 subjects; 61.4%). The mean time since first diagnosis of liver cirrhosis score was 1665.5 days.

Hepatitis C was the most common liver cirrhosis etiologic category (242 subjects; 46.9%) with “alcoholic liver disease” reported as the second most common (220 subjects; 42.6%). The majority of subjects did not have HE or diabetes at Screening (364 subjects; 70.5%). In general, the balance in baseline disease characteristics across all 6 treatment groups was consistent.

The primary objective of this study was to assess the efficacy of rifaximin SSD versus placebo in preventing complications of liver cirrhosis and all-cause mortality in subjects with early liver decompensation.

Treatment with rifaximin IR and SER SSD was shown to be safe and well-tolerated and demonstrated potential therapeutic utility, particularly the IR 40 mg QHS and SER 80 mg QHS formulas, in preventing complications of liver cirrhosis and all-cause mortality in patients with early liver decompensation.

While the primary analysis did not demonstrate statistically significant differences in time to composite endpoint of hospitalization for the liver cirrhosis complications or mortality up to 24 weeks for the combined rifaximin SSD groups versus placebo ($p = 0.8062$) or any pairwise comparison, in a post-hoc analyses there was a consistent pattern of benefit with rifaximin SSD IR 40 mg and SSD SER 80 mg.

The IR 40 mg group post-hoc analysis revealed a statistically significant difference versus placebo ($p = 0.0297$) for the composite endpoint of all-cause hospitalization/all-cause mortality (primary endpoint of the study was hospitalization for any of the liver cirrhosis complications (HE, EVB, SBP, or HRS) ([RNLC2131 CSR Appendix 16.1.13](#))). In addition, subjects in the alcohol-induced only subgroup had a statistically significant difference in time to All-cause Hospitalization/All-cause Mortality versus placebo when treated with rifaximin IR 40 mg QHS ($p = 0.0298$). Furthermore, subjects with a Conn score of 0 demonstrated a statistically significant difference for both the overall treatment comparison of any rifaximin SSD treatment versus placebo and predominantly in favor of the IR 40 mg formulation.

Results of the sensitivity analysis on the PP population demonstrated a statistically significant difference in the time to hospitalization for any of the liver cirrhosis complications or all-cause mortality up to 24 weeks that was in favor of the SER 80 mg QHS treatment group versus placebo ($p = 0.0464$). Based on the Kaplan-Meier estimates, the SER 80 mg QHS group presented with the highest survival rate of all treatment groups for Time to Hospitalization for Any of the Liver Cirrhosis Complications by Treatment Group, however this effect was not statistically significant.

A trend was observed in the time to hospitalization for any of the liver cirrhosis complications or all-cause mortality during the 24 week period within the ≥ 947 days subgroup in favor of the SER 80 mg QHS group versus placebo (stratified log-rank $p = 0.0517$). In addition, subjects in the alcohol-induced only subgroup had a statistically significant difference in time to All-cause Hospitalization/All-cause Mortality versus placebo when treated with rifaximin SER 80 mg QHS ($p = 0.0166$).

The safety outcomes were consistent with the known safety profile of rifaximin. Treatment-emergent AEs, SAEs, severe TEAEs, and drug-related TEAEs occurred most frequently in the GI disorder System Organ Class (SOC).

Hepatic encephalopathy was the most common preferred term (PT) followed by ascites, edema peripheral, and diarrhea. No deaths were related to study drug. Overall, there were no clinically relevant differences observed at SOC and PT levels between groups.

3.4 Rationale

3.4.1 Scientific Rationale for the Use of Rifaximin in Preventing Major Complications of Liver Cirrhosis:

Multiple lines of clinical and experimental evidence support the use of rifaximin in preventing complications of cirrhosis through mechanisms that:

- decrease serum neurotoxin production
- decrease endotoxin production and absorption
- reduce intestinal bacterial translocation (BT)
- reduce intestinal permeability
- decrease portal venous pressures through reduction in endotoxin concentrations
- activate the nuclear pregnane X receptor (PXR)

Rifaximin is a nonaminoglycoside, semisynthetic antibiotic derived from rifamycin. It is a non-systemic, poorly-absorbed, oral antibiotic specific for enteric pathogens of the GI tract ([Xifaxan® PI, Gerard 2005, Gillis 1995, Hoover 1993](#)). Rifaximin has potentially important advantages in preventing the complications of cirrhosis relative to orally bioavailable, broad-spectrum antibiotics. For example, rifaximin has minimal systemic exposure regardless of food intake or presence of GI disease which mitigates the risk of systemic side effects. Neither a reduction in overall colonic bacteria nor an increase in antimicrobial resistance in the colonic bacteria occurs to a clinically significant extent.

Furthermore, *in vitro* studies have demonstrated that rifaximin interferes with the transfer of and promotes the elimination of plasmids from various Gram-positive and Gram-negative bacterial hosts, suggesting that rifaximin is capable of limiting the transfer of antibiotic-resistance plasmids and the diffusion of virulence factors in bacteria ([Debbia 2008](#)).

The use of rifaximin in the treatment of complications of cirrhosis is supported by microbiological and pharmacodynamic evidence which suggests both effects on bacteria and on host inflammatory response as mechanisms of action as outlined below:

Rifaximin is active against the bacteria that have been investigated as possible pathogenic agents for SBP ([Xifaxan® PI, Gerard 2005](#), [Gillis 1995](#), [Hoover 1993](#)).

Rifaximin affects bacterial translocation to mesenteric lymph nodes ([Fiorucci, 2002](#)).

Rifaximin induces in enteroaggregative and enterotoxigenic *Escherichia coli* a loss of virulence factors such as enterotoxins, surface adhesion factors and matrix metalloproteinase-9 (MMP-9), and changes in epithelial cell physiology associated with reduction in bacterial attachment/internalization ([Brown 2010](#); [Fiorucci 2002](#)).

Data indicate that the anti-inflammatory activity of rifaximin is due to its gut-specific human PXR activation ([Ma 2007](#)). Activation of PXR, such as that observed with rifaximin in the intestinal lumen, results in upregulation of metabolic enzymes and transporters (e.g., CYP3A, sulfotransferases, and P-glycoprotein) that may result in increased epithelial cell protection against bacterial metabolic products.

3.4.2 Study Rationale

Cirrhosis is a major cause of CLD in the US and is the 12th leading cause of death. The incidence of cirrhosis in the US is increasing and will continue to be a major health burden from an economic and societal/caregiver perspective. While liver transplant is the only curative therapy for cirrhosis; safe, effective, and cost-efficient therapies for the prevention of the major complications of cirrhosis including mortality, and to bridge a patient to transplant are needed. These therapies must arrest the hemodynamic and infectious etiologies of cirrhosis complications, and improve the morbidity, mortality, and quality of life of the patient.

Rifaximin is approved by the United States Food and Drug Administration (FDA) to reduce the risk of OHE recurrence in patients ≥ 18 years of age. It is not indicated for primary prophylaxis of HE events.

The current literature supports the potential therapeutic utility of rifaximin in treating complications of cirrhosis with ascites such as SBP, HE, EVB, and HRS through multiple mechanisms including direct suppression of intestinal bacterial overgrowth (IBO) and bacterial translocation (BT) that leads to a reduction in endotoxemia, bacteremia, and bacterial seeding of ascitic fluid, and indirect improvement in portal hemodynamics. While the efficacy of broad spectrum antibiotics for the treatment and prophylaxis of cirrhosis complications such as SBP is well documented, they have high systemic exposures and there is concern over the emergence of drug-resistant organisms.

The new rifaximin SSD IR and SER are novel formulations of rifaximin that are designed to improve luminal solubility to increase the availability of soluble rifaximin to the gut lumen and epithelia, while minimizing systemic exposure. Its unique formulation greatly improves its water solubility without the need for bile acids, an important determination of solubility of the current approved formulation ([Darkoh 2010](#)).

This characteristic makes the new SSD formulation particularly attractive for use in a population with significantly impaired hepatic function. Data from early phase trials with the SSD formulation support the safety, solubility and potential clinical utility of rifaximin in preventing complications of cirrhosis in patients with early liver decompensation. Based on these data and the medical need for safe and effective treatments for OHE, the Sponsor is seeking to initiate clinical development of Rifaximin SSD in OHE.

The current standard of care for patients with hepatic encephalopathy is treatment with nonabsorbable disaccharides lactulose or lactitol, which decreases the absorption of ammonia through cathartic effects and by altering colonic pH. In addition to lactulose, oral antibiotics have been used in OHE to reduce ammonia-producing enteric bacteria. However, because of side effects these agents are only infrequently used at present.

Rifaximin is currently approved for reduction in risk of OHE recurrence, but not for the treatment of OHE. Randomized clinical trials showing the superiority of rifaximin plus lactulose versus lactulose alone suggest that rifaximin may be useful in the treatment of OHE. Based on these data and the need for safe and effective alternatives to systemic broad spectrum antibiotics used to treat complications of cirrhosis, this Phase 2 dose-ranging trial will be conducted to assess the viability of rifaximin SSD for the prevention of complications in cirrhosis patients with early decompensation.

4.0 OBJECTIVES

4.1 Efficacy Objectives

4.1.1 Primary Objective

The primary objective of this study is to assess the efficacy of rifaximin SSD [40 mg immediate release (IR) and 80 mg sustained extended release (SER)] plus lactulose versus placebo plus lactulose for the treatment of OHE.

4.1.2 Secondary Objectives

The secondary objectives of this study are to:

- Assess the safety of rifaximin SSD in subjects with OHE.
- Assess the effects of treatment with rifaximin SSD on key secondary endpoints.

5.0 STUDY DESIGN

5.1 Description of Study Design

Study RNHE2041 is a Phase 2, randomized, double-blind, placebo controlled, multicenter study evaluating the efficacy and safety of rifaximin SSD tablets (40 mg IR and 80 mg SER) plus lactulose in subjects hospitalized with OHE. Subjects who have liver cirrhosis and OHE, defined as a score of 2 or 3 on the Hepatic Encephalopathy Grading Instrument [[\(HEGI\); Appendix A](#)], are eligible for enrollment. Subjects who successfully meet the inclusion/exclusion criteria will enter the treatment period and will be randomized in a 1:1:1:1:1 ratio into 1 of 5 treatment groups as noted below. The blinded treatment period starts upon randomization following hospital admission.

Subjects will be on blinded treatment for up to 14 days. All subjects who complete the blinded randomized treatment phase (defined as confirmed resolution of OHE), will continue on to the safety follow-up period and receive 30 days of open-label treatment with Xifaxan® 550 mg upon hospital discharge, regardless of the treatment arm to which they were previously randomized. If subjects remain hospitalized following OHE resolution, standard of care treatment (which may include Xifaxan® 550 mg) should be given until hospital discharge. Open-label drug should only be dispensed to subjects upon hospital discharge. Please note this may be on a different day than OHE resolution.

- Treatment A: 40 mg immediate release (IR) rifaximin SSD tablet once daily (QD) and lactulose*.
- Treatment B: 40 mg immediate release (IR) rifaximin SSD tablet twice daily (BID) and lactulose*.

- Treatment C: 80 mg sustained extended release (SER) rifaximin SSD tablet once daily (QD) and lactulose*.
- Treatment D: 80 mg sustained extended release (SER) rifaximin SSD tablet twice daily (BID) and lactulose*.
- Treatment E: SSD placebo tablet twice daily (BID) and lactulose*.

*Oral Lactulose will be administered according to the product label, with dosage adjusted to produce 2 to 3 soft stools daily or per PI discretion. Rectal lactulose may be administered in lieu of oral lactulose. Bristol stool type will still be assessed as required by the protocol for subjects dosed with rectal lactulose. Dose amount and frequency for oral and rectal lactulose should be administered according to the product label or per PI discretion.

An interim analysis will be conducted when at least 10 subjects per treatment group have completed participation in the blinded treatment period of the study. The unblinded interim results will be reviewed by a few designated members of the Sponsor's team who do not have direct involvement with the ongoing study. The interim results will not be shared outside of the small designated team, and no changes will be made to the ongoing study based on the interim study results.

5.2 Selection of Study Population

Approximately 325 subjects (65 subjects per arm), from approximately 60 study sites in the US, hospitalized for liver cirrhosis and OHE, with a HEGI score of 2 or 3 following adequate hydration and lactulose treatment, will be enrolled in this clinical investigation. Expansion to other countries may be considered.

5.2.1 Eligibility

5.2.1.1 Inclusion Criteria

A subject will be eligible for inclusion in this study if he/she meets all of the following criteria:

1. Male or female at least age 18 or older at the time of consent.
2. Female subjects of childbearing potential, defined as fertile following menarche, must have a negative serum pregnancy test at screening and agree to use an acceptable method of contraception throughout their participation in the study. NOTE: Serum pregnancy tests performed upon hospital admission, prior to time of consent, may be used at Screening. Acceptable methods of contraception include double barrier methods (condom with spermicidal jelly or a diaphragm with spermicide), hormonal

methods (e.g., oral contraceptives, patches or medroxyprogesterone acetate), or an intrauterine device (IUD) with a documented failure rate of less than 1% per year. Abstinence or partner(s) with a vasectomy may be considered an acceptable method of contraception at the discretion of the investigator. See [Section 5.2.2](#) for additional information.

Note: Female subjects who have been surgically sterilized (e.g., hysterectomy or bilateral tubal ligation) or who are postmenopausal (defined as a total cessation of menses for > 1 year) will not be considered “female subjects of childbearing potential”.

3. Subject is hospitalized with encephalopathy secondary to liver cirrohis and has a confirmed diagnosis of OHE at Baseline. .
4. Subject has a Grade 2 or Grade 3 HE episode according to the HEGI ([Appendix A](#)) following: a) at least one lactulose treatment with subsequent bowel movement(s) and b) be adequately hydrated (IV fluids at PI discretion).
5. Surrogate decision-maker must be able to read, understand, and provide written informed consent on behalf of the subject on the Institutional Review Board (IRB)/Ethics Committee (EC) approved ICF and provide authorization as appropriate per local privacy regulations.
6. Subject must be able to swallow oral medication (e.g., study drug) without assistance at Baseline.

5.2.1.2 **Exclusion Criteria**

A subject will not be eligible for inclusion in this study if any of the following criteria are met:

Current or Past Medical History

1. Subject has an uncontrolled major psychiatric disorder including major depression or psychoses, as determined by the investigator ([Diagnostic and Statistical Manual of Mental Disorders, 5th., American Psychiatric Association, 2013](#)).
2. Subject has sepsis, as determined by the investigator.
3. Subject is currently taking oral antibiotics, which cannot be discontinued or changed to parenteral at time of enrollment. Note: Subjects currently taking rifaximin who discontinue use at time of enrollment are not excluded.
4. Subject shows presence of intestinal obstruction or has inflammatory bowel disease.

5. Subject has uncontrolled Type 1 or Type 2 diabetes as determined by the investigator.
Note: Subjects with controlled diabetes may be enrolled if they are on stable doses of insulin or oral hypoglycemic drugs for at least 3-months prior to screening, and demonstrate clinically acceptable blood glucose control upon admission in the opinion of the investigator.
6. Subject has an active malignancy (exceptions: non-melanoma skin cancers).
7. Subject has HCC, history of HCC, or reasonable clinical suspicion of HCC per PI.
Prior imaging completed within 6 months prior to obtaining consent may be used to rule out HCC. In lieu of recent imaging, if AFP is above the upper limit of normal cross-sectional imaging techniques should be used to rule out HCC..
8. Subject has any condition or circumstance, as determined by the investigator, (including alcohol or substance abuse) that adversely affects the subject or could cause noncompliance with treatment, or may affect the interpretation of clinical data, or may otherwise contraindicate the subject's participation in the study.
9. If female, subject is pregnant, at risk of pregnancy, or is nursing.
10. Known human immunodeficiency virus (HIV) infection.
11. Subject has undergone a liver transplant within 5 years prior to Baseline.
12. Subject is an employee of the site that is directly involved in the management, administration, or support of this study or is an immediate family member of the same.
13. Subject has a history of hypersensitivity to rifaximin, rifampin, rifamycin antimicrobial agents, or any of the components of rifaximin SSD.
14. Subject used any investigational product or device within 30 days or 5 drug half-lives (whichever is longer) prior to Baseline.
15. Subject used milk thistle or any known P-gp inhibitor within 30 days prior to Baseline.

Subject Withdrawal Criteria

All premature discontinuations and their reasons must be carefully documented by the investigator on the final eCRF, and if need be, on the AE form. Reasons for study completion/discontinuation as listed on the report form are described as follows:

- **Normal Study Completion** – subject completes study as planned per the protocol
- **Adverse Event** – complete AE form

- **Subject Request** – consent withdrawal (i.e. subject moved, schedule conflicts)
- **Protocol Violation** – contact the Sponsor or Sponsor's designee prior to making decision
- **Lost to Follow-Up** – document with two phone calls and a certified letter
- **Pregnancy** – subject will discontinue study drug immediately, but will be followed to term; pregnancy form must be completed
- **Worsening Condition** – subject requires alternate treatment prior to completing the study and the investigator determines it is not due to lack of efficacy (i.e. requires liver transplant during the study).
- **Other** – specify in the comments section of final eCRF

Subjects who terminate treatment early will be asked to complete all end of study visit assessments (see [Section 8.3.1](#) for additional information) prior to commencement of any alternative medication or therapy (if possible). Subjects who discontinue from the study during the treatment period will be asked to come back for the 30 day post-treatment cessation follow-up visit.

All subjects are free to withdraw from participating in this study at any time and for whatever reason, specified or unspecified, and without prejudice. No constraints will be placed on ordinary subject management, and subjects, when appropriate, will be placed on other conventional therapy upon request or whenever clinically necessary as determined by their physician.

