Endpoints: Efficacy Phase Primary: 
• Time to OHE resolution determined using the Hepatic Encephalopathy Grading Instrument (HEGI). Secondary: 
• Time to OHE resolution defined as a West Haven Criteria (WHC) score of 0 or 1• Time to 1 unit decrease in WHC score during the randomized treatment period.• Change from Baseline in WHC score at Day 15 or end of blinded treatment period, whichever occurs first.• Change from Baseline in HEGI score at Day 15 or end of blinded treatment period, whichever occurs first.• Time to improvement in HEGI score.• Length of hospitalization from baseline to end of blinded treatment phase. Safety: 
• Incidence of treatment-emergent adverse events (TEAEs).• Change from baseline to OHE resolution in vital sign measurements and clinical laboratory values• Incidence of infections, (e.g., spontaneous bacterial peritonitis (SBP), urinary tract infection, pneumonia, bacteremia, and cellulitis) Open-label Safety Follow-up Phase: 
• Reoccurrence of OHE during the 30 day follow-up period.• Readmission to hospital during the 30 day follow-up period.• Change from Baseline to study exit in indices of Health Outcome using the Caregiver Burden Inventory (CBI)• Change during Follow-up Phase (from first follow-up visit post OHE resolution to study exit) in Chronic Liver Disease Questionnaire (CLDQ).

Methodology:

This is a randomized, double-blind, placebo-controlled study of Rifaximin SSD in male and female subjects hospitalized with OHE. There will be two treatment phases: (1) a safety and efficacy phase in which blinded treatment will be either (a) rifaximin SSD and lactulose or (b) placebo and lactulose; and (2) an open-label safety follow-up phase where all subjects will receive 30 days of treatment with Xifaxan® 550 mg BID.

There will be five cohorts of 65 subjects each.

- **Cohort 1 (Treatment A)** will enroll 65 subjects with OHE, to be administered 40 mg immediate release (IR) rifaximin SSD once daily (QD)* and lactulose**.
- **Cohort 2 (Treatment B)** will enroll 65 subjects with OHE, to be administered 40 mg immediate release (IR) rifaximin SSD twice daily (BID) and lactulose**.
- **Cohort 3 (Treatment C)** will enroll 65 subjects with OHE to be administered 80 mg sustained extended release (SER) rifaximin SSD once daily (QD)* and lactulose**.

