All Subject assessments will be performed by a trained and qualified Evaluator. Efforts should be made to have the same evaluator assess the same Subject for as many HEGI assessments as possible. Every effort must be made for the same Evaluator to conduct the HEGI assessments at both the resolution of OHE and the confirmation of resolution assessed 3 to 12 hours later.

¹Evaluator, defined by only licensed physicians, physician's assistants or nurse practitioners, who are trained in these instruments may conduct the assessment.

²Assessments are conducted twice per day, approximately 12 hours (±2 hours) apart. Following resolution of OHE, a confirmatory HEGI (3 to 12 hours post initial resolution) must be done to complete the blinded randomized treatment phase.. Subjects should continue to dose on blinded study medication until OHE resolution is confirmed.

³Subject will report on lactulose use (if any) and open-label dosing compliance from previous visit to current visit. Diary cards are not being used on this study.

⁴Open-label Safety Follow-up visits will be conducted by a study investigator.

⁵Clinical laboratory tests run within 24 hours of consent, may be used in place of drawing new labs at Screening provided all protocol required labs are present. Note: AFP is only required at Screening.

⁶ Serum pregnancy test is done at Screening and urine pregnancy test at EOS visit (open-label safety follow-up Visit 3)

⁷ Open-label drug should only be dispensed to subjects upon hospital discharge. Please note this may be on a different day than OHE resolution.

⁸ If a subject early terminates/discontinues during the study, the visit schedule at the end of the that treatment phase should be followed for their ET visit.

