8.1.3 OHE Resolution

The following procedures will occur upon OHE resolution with confirmatory HEGI.

- Record all concomitant medications and AEs.

Clinical Study Protocol, Amendment 3, dated 08 January 2020

CONFIDENTIAL

Page 42

- Collect vital sign measurements (include weight, supine blood pressure, heart rate, respiration rate, and temperature).
- Complete a full physical examination, including evaluation for complications of liver cirrhosis.
- Collect blood and urine for clinical laboratory tests (hematology, blood chemistry, and urinalysis).
- Determine and record HEGI score. ([Appendix A](#))
- Determine and record WHC score. ([Appendix B](#))
- Dispense Xifaxan® 550mg (BID dosing) and review dosing instructions with subject.
- Schedule and review the open-label safety follow-up visits with subject.
- Record stool appearance. ([Bristol, Appendix E](#))

If the subject discontinues or early terminates from the study prior to starting the open-label safety follow-up period, the OHE Resolution visit assessments are to be done as the subjects early termination/discontinuation visit and the subject exited from study. Please refer to [Section 8.3.1](#) for a list of early termination/discontinuation procedures to be conducted.

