9.3.1 Time Period for Detecting and Reporting of AEs and SAEs

From the time of informed consent through study completion/early termination, including the 30-day open-label safety follow-up period.

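### Discontinuers have conflicting follow-up instructions and subjects unresolved at Day 15 have no scheduled safety visit, so scheduled 30-day ascertainment of SAEs and deaths depends on the primary outcome

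*Combined protocol and SAP*

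**What the plan says.** **Subjects who leave during blinded treatment.** The Subject Withdrawal Criteria, after the exclusion list in section 5.2.1.2, state: "Subjects who discontinue from the study during the treatment period will be asked to come back for the 30 day post-treatment cessation follow-up visit". For a subject who leaves before the open-label period, section 8.1.3 says that "the OHE Resolution visit assessments are to be done as the subjects early termination/discontinuation visit and the subject exited from study". Footnote 8 of Table 1 provides for a single early-termination (ET) visit: "the visit schedule at the end of the that treatment phase should be followed for their ET visit". Section 8.3.1 lists the assessments at that visit and no later contact.

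**Subjects who reach the end of 14 days unresolved.** Section 5.1 states: "All subjects who complete the blinded randomized treatment phase (defined as confirmed resolution of OHE), will continue on to the safety follow-up period". Sections 8.1.5 to 8.1.7 time all three follow-up visits from confirmed resolution. The synopsis and section 7.5.4, however, speak of subjects who complete the randomized period without resolution, and censor them at 14 days. No section gives these subjects a next visit or an exit status.

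**Safety collection.** Section 9.3.1 sets the window for AEs and SAEs: "From the time of informed consent through study completion/early termination, including the 30-day open-label safety follow-up period". Section 9.4 adds that any SAE within 30 days of stopping study drug is reportable, whatever its cause, if the investigator learns of it. Section 9.7 follows AEs already open, and section 8.2 allows post-study visits for them. Section 7.5.5 tabulates SAEs and fatal TEAEs as counts or percentages by group.

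**The concern.** A site cannot carry out both instructions for a discontinuer, and the 30-day visit that one of them names has no place in any schedule and no list of assessments. The non-resolver falls between two uses of the word complete. In section 5.1 it means confirmed resolution; in the censoring rule it includes subjects who never resolved.

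The consequence is statistical as well as operational. Whether a subject is actively looked at over the following 30 days depends on whether the primary event occurred. If treatment works as assumed, the arms differ in how thoroughly late SAEs and deaths are sought. Section 7.5.5 gives a start date for treatment-emergent events but no closing date, and makes no allowance for unequal observation, so the tables by arm would not show the difference.

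**Working it through.** **1. Texts side by side**

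| Subject | Scheduled contact after blinded treatment | Source |
|---|---|---|
| Confirmed resolution | Days 7, 14 and 30 after resolution | 5.1, 8.1.5 to 8.1.7 |
| Leaves the study during blinded treatment | A 30-day post-cessation visit, or none after the early-termination visit | 5.2.1.2 against 8.1.3, Table 1 footnote 8 and 8.3.1 |
| Unresolved at the end of 14 days | None stated | 5.1, 7.5.4, 8.1.5 to 8.1.7 |

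The conflict in the second row concerns subjects who discontinue from the study. The withdrawal text deals with those who only stop treatment early in a separate sentence.

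**2. The plan's own figure.** Section 7.3 gives 61 evaluable subjects per group for at least 80% power, two-sided 0.05, with 76% against 51% resolved. With exponential times the hazard ratio is ln(0.24)/ln(0.49) = 2.00. Expected events in two groups of 61 are 122 × (0.76 + 0.51)/2 = 77.5. Power is then 86% by Schoenfeld's formula, 84% by Freedman's and 83% by a pooled comparison of proportions. The power statement is therefore true. None of these formulas returns 61 exactly (they give 52, 56 and 58 per arm), but nothing below depends on that number.

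**3. Subjects without scheduled 30-day follow-up.** Inputs are 76% and 51% (section 7.3) and 65 randomized per arm (section 5.2). The percentages are read as applying to everyone randomized.

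- Per active arm: 65 × (1 − 0.76) = 15.6, or 24%
- Placebo arm: 65 × (1 − 0.51) = 31.9, or 49%
- All five arms: 4 × 15.6 + 31.85 = 94.3 of 325, or 29%

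These are upper figures. The 24% and 49% are everyone not resolved within 14 days, so they include anyone who died or withdrew unresolved before Day 15. Early discontinuers without resolution should not be added on top.

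**4. Mean scheduled follow-up after blinded treatment.** 30 × 0.76 = 22.8 days on active and 30 × 0.51 = 15.3 days on placebo, counting non-resolvers as zero.

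**5. Effect on a tabulated percentage.** Let p be the proportion resolved, r and q the 30-day event risks in resolvers and non-resolvers, and s the share of non-resolvers' events that passive reporting finds. Assume that resolvers' events are all found. The true proportion is p·r + (1 − p)·q and the tabulated one is p·r + (1 − p)·q·s, so the shortfall is (1 − p)·q·(1 − s). That is 0.24·q·(1 − s) on active and 0.49·q·(1 − s) on placebo. With the same q and s in both arms, the placebo shortfall is 0.49/0.24 = 2.04 times the active one. It is zero if s = 1, and equal in the two arms if p is equal. The documents give neither q nor s for these subjects, so no number of events is offered.

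**The case against.** **Passive capture exists.** A reader might infer that non-resolvers and discontinuers are not followed at all. The documents do not support that. Section 9.4 covers SAEs, deaths included, for 30 days after study drug is stopped in every arm. Section 9.3.2 covers later related SAEs, and sections 8.2 and 9.7 cover open AEs. This stands: ascertainment is weaker, not absent. But none of these provisions creates a contact that would reveal a new event after exit.

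**A count of missed deaths.** A reader might multiply the non-resolvers by the 18% mortality for hepatic encephalopathy in section 3.1.1. That figure comes from a series of hospital admissions for cirrhosis. It is not a 30-day risk after 14 days of trial treatment, and this trial excludes sepsis and hepatocellular carcinoma. Deaths before Day 15 would also be counted twice, although daily recording in hospital already covers them. Nor do the documents state that non-resolvers are at higher risk; that is a plausible inference only.

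**Bias as a certainty.** The imbalance between arms is conditional on the planning rates. In addition, the safety summaries are descriptive, and resolvers in every arm are assigned open-label Xifaxan after discharge, so late comparisons by randomized arm are limited in any case. Both points stand. They lower the stakes but do not remove the unequal observation.

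**The synopsis.** It describes an "open-label safety follow-up phase where all subjects will receive 30 days of treatment with" Xifaxan. A reader might take this as a contradiction of section 5.1. The same synopsis later restricts entry to subjects with confirmed resolution and to those who continue, so this is loose wording to align and not a separate conflict.

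**Conclusion.** The point holds in a limited form. The instructions for subjects who discontinue during blinded treatment conflict, and the 30-day visit is in no schedule. The status of subjects unresolved at 14 days is undefined, and they have no scheduled safety visit. For both groups, new SAEs and deaths after that point depend on the investigator becoming aware of them.

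If 76% and 51% hold, up to 24% of active and 49% of placebo subjects, at most about 94 of 325, would lack scheduled 30-day follow-up. Any under-counting would then fall mainly on placebo. The textual conflict and the scheduling gap do not depend on any assumed rate; the difference between arms does, and it vanishes if resolution rates are equal. The primary efficacy analysis is not affected, since it stops at 14 days.

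**What to change.** Reconcile sections 5.1, 5.2.1.2 (Subject Withdrawal Criteria), 8.1.3, 8.3.1, 9.3.1 and Table 1 footnote 8 into one follow-up rule that names discontinuers and non-resolvers separately, and align the synopsis wording. Use one meaning of completion throughout. This concerns data collection only and need not prescribe any treatment.

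State in section 9.3.1 that SAEs and vital status are actively ascertained over the same 30 days after the last blinded dose for every dosed subject who has not withdrawn consent to contact. State in section 7.5.5 that SAEs and deaths are tabulated by arm over that window. For resolvers, blinded dosing continues until resolution is confirmed, so Visit 3 at 30 ± 2 days falls at about the end of the window.

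The cost is protocol wording and one contact for each non-resolver or discontinuer, by telephone or at the visit that the withdrawal text already names. On the planning rates that is at most about 94 contacts among subjects not resolved by 14 days. The protocol already uses a 30-day horizon for SAE reporting, so no new time frame is introduced.
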